10. STATISTICAL ANALYSIS

All statistical analyses will be performed using SAS Enterprise Guide 7.1 (SAS Institute Inc., Cary, NC, USA), provided by HIRA through a virtual access machine.

Phase I of the study (descriptive)

Main Analysis

- Descriptive analysis will be conducted separately in two cohorts of non-cancer VTE and cancer VTE patients according to co-presence of active cancer.
- Sociodemographic and clinical characteristics will be summarized with means (standard deviations [STD]) or median (interquartile range [IQR]) for continuous variables and with count (proportions) for categorical variables for the three treatment groups of interest: PAC only (UFH, LMWH, UFH+LMWH), warfarin-based (warfarin, PAC/warfarin) group, NOAC-based (NOAC, PAC/NOAC) group. NOAC-based (NOAC, only group, PAC/NOAC) group. Analysis of variance, and chi-square test will be conducted for continuous variables, and categorical variables, respectively.
 - In order to distinguish between PAC bridging therapy and PAC treatment, we will apply a time restriction of 2 weeks to PAC bridging therapy.
- Temporal trend in anticoagulation therapy for VTE will be presented between 1 Mar 2013 and 30 Jun 2019. Proportions of the index OACs will be estimated according to calendar year and quarter.
- The number and percentage of patients who discontinue treatment completely, experience treatment interruption and treatment switch during their follow-up will be described by the index anticoagulant treatment received. Results will be limited to the first of each of these events for each patient. For patients experiencing a treatment switch, the new treatment will be described at the time of their first switcher per individual drug.
- The duration of the index treatment by the index anticoagulant treatment received will also be summarized in terms of days using descriptive statistics (mean [STD], median [IQR]).
- The Kaplan-Meier method will be applied to derive the empirical distribution of time to each of the treatment endpoints of interest (e.g., treatment discontinuation or switch); these analyses will be performed per index anticoagulant treatment received and no comparisons will be made. Log-rank test will be conducted at the 3-, and 6 months after treatment initiation to assess statistical significance between the survival curves. Persistent rate will also be calculated at the same time point.
- In the NOAC-based group, all analyses will be repeated stratified by each individual NOAC class (e.g, apixaban, dabigatran, rivaroxaban, edoxaban) to

PFIZER CONFIDENTIAL

identify the difference in baseline characteristics and treatment patterns between each NOAC class.

- To identify potential reasons for treatment change, clinical events preceding the first treatment change (major bleeding, thromboembolism diagnosis, complications of VTE, major surgery, active cancer, a new diagnosis of CKD or AKI, a new diagnosis of liver disease or abnormal liver function) will be measured within 30 days prior to the first date of treatment change. Patients can contribute with multiple events.
- All analyses of treatment patterns will be presented stratified according to the index anticoagulant treatment, and not overall or per drug class.

Phase II of the study (comparative)

Propensity score analysis

- To balance and adjust for any potential differences in baseline sociodemographic and clinical characteristics between treatment groups, propensity score (PS) methods will be implemented.
 - A logistic regression model will be used to estimate the predicted probability (propensity) of initiating each NOAC compared with warfarin given baseline covariates mentioned above. By using the estimated PS, we will apply the PS based on the inverse probability of treatment weights (IPTW), where the treatment group of interest will be given a weight of 1/PS, and the comparator group will be given a weight of 1/(1-PS) [4, 5]. The most extreme 1% of PS values (IPTW with trimming) will be excluded to improve comparability between exposure groups.

Main Analysis

- Sociodemographic and clinical characteristics will be summarized with means (STD) or median (IQR) for continuous variables and with count (proportions) for categorical variables for the two treatment comparisons of: apixaban vs warfarin, rivaroxaban vs warfarin, edoxaban vs warfarin and dabigatran vs warfarin (and NOAC vs NOAC, if scientifically feasible).
 - Differences in baseline covariates between users of different OACs will be assessed using the SD where the absolute SD <0.1 will be considered as well balanced.
- The incidence rate of major bleeding overall and by site will be presented as the total number of events per 1,000 person-years, with its 95% CIs estimated using the Poisson distribution.
- The risk of major bleeding according to the treatment of interest will be investigated in time-to-event analyses using standard Kaplan-Meier methods.

- Cox proportional hazards model will be used to compare the safety outcome between users of different OACs, weighted on the estimated PS according to the IPTW approach.
 - Proportionality assumption will be tested by use of Schoenfeld residuals.

Subgroup Analysis

- The potential heterogeneity of treatment effects in selected subgroups of patients with VTE will be examined for the major bleeding as follows:
 - Aged <65 years vs. aged \geq 65 years
 - Females vs. males
 - Setting of VTE diagnosis (inpatient vs. outpatient)
 - Type of VTE (DVT without PE [ICD-10: I80.2, I80.3] vs. PE with or without DVT [I26.0, I26.9])
 - Major orthopedic surgery-provoked VTE
 - Major orthopedic surgery-provoked VTE is defined as an event preceded by knee arthroplasty, hip arthroplasty, or hip fracture surgery (National Procedure Codes: N0305, N0601, N0611, N0641, N0711, N2070, N0715, N2710, N0731, N0981, N0991, N1711, N3710, N1721, N3720, N1715, N4710, N1725, N4720, N2072, N2077, N2712, N2717, N3712, N3717, N3722, N3727, N4712, N4717, N4722 or N4727) within 3 months period prior to index date
 - With vs. without CKD stage 3 or 4 (N18.3, N18.4)
- P-for-interaction value <0.05 will be used to denote a significant difference between the two groups.

Sensitivity Analysis

- Vary the definition of treatment interruption/discontinuation to 15 and 60 days (allowing for varying non-adherence) to assess the effect this had on study outcomes.
- Four other approaches involving PS will be applied to determine the robustness of our study findings. First, we will vary the extreme value of PS in trimming process (most extreme 5%, and 10% will be excluded). Second, we will include the estimated PS, in addition to other covariates, into our multivariable Cox proportional hazards regression model. Third, we will stratify on the estimated PS in deciles. Last, we will apply another weighting approach, standardized mortality ratio weights, with the weights given as follows: 1 for the treatment group of interest and PS/(1 – PS) for the comparator group.[4]

- Exclude patients with a history of bleeding during the 6-month pre-index-date period in Phase II comparative analysis to evaluate the robustness of findings with respect to changes in underlying risk of patients

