- Had a record of active cancer, defined as first diagnosis of cancer with V code (a special code applied to patients with confirmed diagnosis of cancer by Korean Ministry of Health and Welfare for reimbursement for 5 years or longer if recurrent/metastatic) within the past 6 months of period prior to index date; or receiving anti-cancer treatment (chemotherapy, radiation therapy, or cancer-related surgery) under cancer diagnosis with V code within the past 6 months period prior to index date

Follow-up

- **Phase I of the study:** Patients will be followed-up from the index date until the earliest of in-hospital death or end of the study period (31 Dec 2019).
- **Phase II of the study:** Patients will be followed-up from the index date until the earliest of outcome occurrence (bleeding event), treatment discontinuation, switch to another anticoagulant, in-hospital death, or end of the study period (31 Dec 2019), where patients will be considered to have discontinued treatment when new prescription is absent within the 30-day grace period after the end of the former prescription.

- **Variables**

Exposure(s)

- Anticoagulant therapy (PAC [LMWH, UFH, others], NOACs [apixaban, dabigatran, rivaroxaban, edoxaban], warfarin).

Outcome(s)

- **Phase I of the study:** sociodemographic and clinical characteristics of patients with VTE, utilization of index anticoagulant treatment, treatment patterns (including treatment interruption, switching, complete discontinuation), overall treatment duration, and clinical events preceding first treatment change
- **Phase II of the study:** Primary or secondary diagnosis with major bleeding (by site: intracranial, gastrointestinal [GI], and other sites) after the index date

Covariate(s)

- Sociodemographics (age, sex) will be assessed on the index date. Clinical characteristics including comorbidities, previous use of medications, and the number of outpatient visits will be assessed within the 6-month period prior to the index date

- **Data sources**

- South Korea's Health Insurance and Review Assessment Service (HIRA) database

- **Study size**

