8. RESEARCH METHODS

8.1. Study design

A retrospective, observational, nationwide population-based cohort study will be conducted to describe the treatment patterns of anticoagulation therapies prescribed to patients with VTE in South Korea, and assess the risk of major bleeding associated with apixaban and other NOACs use, as compared with warfarin, by using the Health Insurance Review and Assessment Service (HIRA) database from 1 Mar 2012 to 31 Dec 2019 (Figure 1).

Note: HIRA, Health Insurance and Review Assessment service; LMWH, low molecular weight heparin; NOAC, non-vitamin K antagonist; PAC, parenteral anticoagulants; VTE, venous thromboembolism; W, warfarin

[†]Record of active cancer is defined as first diagnosis of cancer with V code within the past 6 months of period prior to index date; or receiving anti-cancer treatment under cancer diagnosis with V code within the past 6-month period prior to index date.

[‡]Warfarin-based and NOAC-based include either PAC with warfarin/NOAC or warfarin/NOAC only

[figure not shown]
Figure 1. Study participants inclusion and exclusion criteria

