8.2. Study population

The study cohort will be defined as patients diagnosed with VTE between 1 Mar 2013 and 30 Jun 2019. The cohort entry will be defined as the date of incident VTE diagnosis. The index date will be defined as the date of first prescription for anticoagulants within 30 days after the index VTE event. The length of the exclusion assessment window will vary depending on the condition, from 12-months at minimum to anytime prior to index date. The following patients will be excluded: A record of VTE diagnosis within the 12-month period prior to the index VTE encounter, diagnosed with atrial fibrillation, atrial flutter, mechanical heart valve replacement or mitral stenosis anytime prior to index date, had a record of Inferior Vena Cava filter anytime prior to index date, received anticoagulatory therapy within the 12-month period prior to index VTE encounter to restrict to new users of anticoagulatory therapy, prescribed two different anticoagulants on the same index date to prevent exposure misclassification, had a record of pregnancy within the 9-month period prior to index date, and for the Phase II of the study only, had a record of active cancer within six months period prior to index date.

Baseline sociodemographic characteristics (e.g., age, sex) will be assessed on the index date, whereas clinical characteristics (comorbidities, previous use of medications, Charlson comorbidity index [CCI], HAS-BLED scores, initial presentation of VTE, number of outpatient visits) will be assessed in the 6-month period prior to the index date except when otherwise specified in section 8.4 *Variables* (Figure 2).

Within this study cohort, we will describe the treatment patterns of anticoagulants prescribed for VTE treatment throughout the period of follow-up, defined as the period from the index date to the end of the study period. Moreover, if feasible, we will also examine the risk of major bleeding overall and by site, associated with each NOAC use, as compared with warfarin.

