8.3.2. Exclusion criteria

Patients meeting any of the following criteria will not be included in the study:

1. Had a record of VTE diagnosis (ICD-10: I26.0, I26.9, I80.2, I80.3) within the 12-month period prior to the index VTE encounter.
2. Diagnosed with atrial fibrillation/flutter (ICD-10: I48), mechanical heart valve replacement (National Procedure Code: Z952, M6531, M6532, M6533, O1781, O1782, O1783, O1791, O1792, O1793, O1797, O1794, O1795, O1796, O1798, O1799) or mitral stenosis (ICD-10: I05.0, I05.2) anytime prior to index date.
3. Had a record of Inferior Vena Cava filter (National Procedure Code: O2045, M6650) anytime prior to index date.
4. Received anticoagulatory therapy within the 12-month period prior to index VTE encounter to restrict to new users of anticoagulatory therapy.
5. Prescribed two different anticoagulants on the same index date to prevent exposure misclassification.
6. Had a record of pregnancy (ICD-10: O03-O07, O10-O14, O16, O20-O026, O28-O36, O41-O43, O46.8, O46.9, O61-O66, O67.8, O67.9, O69, O70-O75, O80-O92, O94-O99, P08, Z33-Z39) within the 9-month period prior to index date.

7. Had a record of active cancer, defined as first diagnosis of cancer (ICD-10: C00-C97 [excluding non-melanoma skin cancer: C44]) with V code (V011, V027, V193, V194; a special code applied to patients with confirmed diagnosis of cancer by Korean Ministry of Health and Welfare for reimbursement for 5 years or longer if recurrent/metastasis) within the past 6 months of period prior to index date; or receiving anti-cancer treatment (chemotherapy, radiation therapy, or cancer related-surgery) under cancer diagnosis with V code within the past 6 months from index date (for Phase II of the study only). WHO-ATC codes and National Procedure Codes for anti-cancer treatment are shown in below table.

Anti-cancer treatment	WHO-ATC codes / National Procedure Codes
Chemotherapy	L01-04, H02AB02, H02AB04, H02AB06, H02AB07, H02AB09
Radiation therapy	HD051-HD059, HD061, HD071-HD073, HD080-HD089, HD091-HD093, HD110-HD115, HD121, HD150, HD160, HD211, HD212, HZ271

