8.4. Variables

Exposure

- **Phase I of the study:** PAC (UFH [Anatomical Therapeutic Chemical [ATC] code: B01AB01], LMWH [B01AB04, B01AB05, B01AB06, B01AB12], VKA (warfarin [B01AA03]), NOACs (apixaban [B01AF02], rivaroxaban [B01AF01], edoxaban [B01AF03], dabigatran [B01AE07])
- **Phase II of the study:** Apixaban (B01AF02), Rivaroxaban (B01AF01), Edoxaban (B01AF03), Dabigatran (B01AE07), Warfarin (B01AA03)

Outcome(s)

- **Phase I of the study**

- Sociodemographic and clinical characteristics of patients with VTE who initiated anticoagulants.
- Utilization of different anticoagulants at treatment initiation. Patients will be classified based on their index anticoagulant treatment received within 30 days after being diagnosed with VTE.
- Treatment interruption from the index anticoagulant treatment, which will be defined as when a patient has a gap with no new treatment within 30 days of the estimated end of supply, but subsequently restarts the index treatment after this period.[1] The time to treatment interruption will be defined as the period from the index date to the date of treatment interruption.
- Treatment switching will be defined as a prescription of another anticoagulant therapy that is started after the treatment initiation of the index anticoagulant treatment and within 30 days after the estimated end of supply of the index anticoagulant drug (exposure to the new anticoagulant treatment must last for at least 30 days to be considered as a treatment switch). The time to treatment switch will be defined as the period from the index date to the date of treatment switch.

Exemption: As heparin can be initiated at acute stage of DVT/PE before clinical decision to use OAC, a switch from initial heparin treatment to an OAC within 2 weeks after heparin treatment initiation will not be considered a treatment switch.

- Treatment discontinuation (complete discontinuation; no reinitiation) will be defined as when a patient who ended their first continuous treatment episode with the index anticoagulant treatment without switching, and subsequently have no further prescriptions for that respective anticoagulant treatment during all available follow-up time. The time to treatment discontinuation will be defined as the period from the index date to the date of treatment discontinuation.
- Overall anticoagulant treatment duration will be defined as the time period from the index date to the earliest of treatment interruption, switch, or discontinuation.

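### Phase I groups heparin-first patients by what happens after the index date, so those who die before an oral anticoagulant always count as PAC only

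*SAP*

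**What the plan says.** **Time zero.** SAP 8.2: "The index date will be defined as the date of first prescription for anticoagulants within 30 days after the index VTE event". For a heparin-first patient this is the heparin date. The Protocol abstract sets Phase I follow-up: "Patients will be followed-up from the index date until the earliest of in-hospital death or end of the study period".

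**Groups.** SAP 10 names them as "PAC only (UFH, LMWH, UFH+LMWH), warfarin-based (warfarin, PAC/warfarin) group, NOAC-based (NOAC, PAC/NOAC) group". The Figure 1 footnote in SAP 8.1 confirms that "Warfarin-based and NOAC-based include either PAC with warfarin/NOAC or warfarin/NOAC only".

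**Rule for heparin-first patients.** SAP 10 says "we will apply a time restriction of 2 weeks to PAC bridging therapy", and Protocol 9.7 has the same sentence. SAP 8.4 adds that "a switch from initial heparin treatment to an OAC within 2 weeks after heparin treatment initiation will not be considered a treatment switch". The same section also says "Patients will be classified based on their index anticoagulant treatment received within 30 days after being diagnosed with VTE".

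**Same-day starts.** SAP 8.3.2 excludes patients with "Prescribed two different anticoagulants on the same index date to prevent exposure misclassification".

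**Outputs.** SAP Tables 5 and 6 set treatment duration, 3- and 6-month persistence, and death side by side for the three groups, without and with active cancer. Protocol 9.7 plans log-rank tests at 3 and 6 months among the three groups. The SAP keeps the test but does not name the groups. In both documents the same bullet says that no comparisons will be made.

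**The concern.** The group label depends on events after the clock starts. Same-day heparin plus OAC is excluded, so every PAC/warfarin or PAC/NOAC patient had to survive from the heparin date to a later OAC date. A heparin-first patient who dies on day 4 is PAC only, whatever treatment was intended. This is immortal time in the bridged part of the OAC-based groups, and the matching early deaths land in PAC only.

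Treatment patterns by index treatment are a primary Phase I objective. A reader of Tables 5 and 6 would take a higher death percentage under PAC only as a feature of those patients or their treatment, when part of it comes from the grouping rule. Neither document has a landmark, a time-varying group or a split into heparin-first and OAC-first patients. The 15- and 60-day sensitivity analysis changes only the grace period.

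**Working it through.** The plan states no Phase I sample size, death rate or bridging rate, so there is no figure of its own to reproduce. The check is in two parts: the logic of the definitions, then the size under assumed values.

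**1. Logic (heparin-first patient, heparin on day 0)**

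| Course | Group |
|---|---|
| OAC on day 5, dies day 10 | OAC-based |
| Dies day 4, no OAC | PAC only |
| Alive at day 14, no OAC by then | PAC only; a later OAC is a switch if the SAP's other switch conditions are met |

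Death before an OAC removes the patient from the OAC-based groups in every case. Nothing moves the other way.

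**2. Size of the artefact in 14-day death**

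Assumptions, none from the documents: 14-day mortality m is 1, 3, 5 or 10% and is the same whatever treatment is planned; planned bridging share b is 60, 80 or 90%; time to OAC is exponential with mean 3 or 7 days; the death hazard is constant to day 14.

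- h = -ln(1 - m)/14; λ = 1/(mean days to OAC)
- P = b · λ/(λ + h) · [1 - exp(-14(λ + h))]: share starting an OAC by day 14 while alive
- A = b · [1 - exp(-14λ)] · (1 - m): share of all who do so and are alive at day 14
- OAC-based death = (P - A)/P; PAC-only death = [m - (P - A)]/(1 - P)

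Example, m = 5%, b = 80%, mean 3 days: h = 0.003664, P = 0.7842, A = 0.7529, P - A = 0.0314. OAC-based: 0.0314/0.7842 = 4.0%. PAC only: 0.0186/0.2158 = 8.6%. The true value is 5% in both.

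Range over the six combinations of b and mean time to OAC:

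| True 14-day death | PAC only | OAC-based | Ratio |
|---|---|---|---|
| 1% | 1.3-2.6% | 0.7-0.8% | 1.63-3.32 |
| 3% | 3.9-7.7% | 2.0-2.4% | 1.62-3.23 |
| 5% | 6.4-12.5% | 3.3-4.0% | 1.61-3.15 |
| 10% | 12.7-23.3% | 6.7-8.1% | 1.58-2.96 |

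**3. Adding OAC-first patients**

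Let half the cohort start on an OAC with the same m = 5%; among the rest, b = 80% and mean 5 days. Then P = 0.7402, A = 0.7138, P - A = 0.0264. OAC-based: (0.5 × 0.0264 + 0.5 × 0.05)/(0.5 × 0.7402 + 0.5) = 0.0382/0.8701 = 4.4%. PAC only: 0.0236/0.2598 = 9.1%. The ratio is about 2.

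**4. Later death, duration and persistence**

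These were simulated with 2,000,000 heparin-first patients per scenario. Further assumptions: 3% death from day 14 to 90, mean time to stopping 120 days, and death counted as the end of treatment.

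| True 14-day death | Measure | PAC only | OAC-based |
|---|---|---|---|
| 1% | median duration (days) | 76.9-78.4 | 79.1-79.2 |
| 1% | 3-month persistence | 44.5-45.2% | 45.4-45.5% |
| 5% | 90-day death | 9.3-15.1% | 6.2-6.9% |
| 5% | median duration (days) | 64.6-72.2 | 75.2-76.3 |
| 5% | 3-month persistence | 40.1-42.8% | 44.0-44.4% |

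**5. The same simulation from day 14**

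With groups fixed at day 14 among survivors, death from day 14 to 90 is about 3.0% in both groups in every scenario. Three-month persistence among those also still on treatment at day 14 is 51-52% in both. The artificial gap disappears.

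**The case against.** **Phase I is descriptive.** It has no prior hypotheses, and death is not among its objectives or listed outcomes. Tables 5 and 6 have no p-value column, and the log-rank test concerns treatment endpoints, not death. As a count of patients who received only heparin, the death row is correct. All of this stands, and it is why the tables should stay. It does not remove the problem, because the rows are laid out by index treatment and the protocol does plan a test among the three groups.

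**Size.** A reader might infer a five-fold excess. Take 1,000 heparin-first patients, 800 planned for an OAC, 3% mortality, and half of the planned-OAC deaths before the OAC: 12/788 = 1.5% against (6 + 12)/(200 + 12) = 8.5%. The documents do not support this as what the tables would show. It is a 14-day risk in heparin-first patients only, and the one-half is arbitrary. The table row runs over the whole of follow-up, and the OAC-based groups also contain OAC-first patients. Both dilute the ratio.

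**Early deaths in general.** PAC only does not absorb all of them. OAC-first patients who die early, and bridged patients who die after starting the OAC, stay OAC-based.

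**Duration and persistence.** A reader might infer a large distortion here too. The effect is small at low mortality. It also depends on whether death ends treatment, is censored or is a competing event, which neither document says.

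**Two windows.** The 30-day and 2-week rules might be read as contradictory, for example with heparin on day 0 and warfarin on day 20. The 30-day sentence can equally be read as repeating the inclusion window, and SAP 8.4 itself carries the 2-week exemption. This is unclear wording, not a proven conflict.

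**Active cancer.** A larger effect in Table 6 would follow if early mortality is higher there, but the documents give no figure for that.

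**Conclusion.** The concern holds for heparin-first patients. The definitions make group membership depend on survival after time zero: deaths before any OAC always fall in PAC only, and bridged patients carry up to 14 days of guaranteed survival. The comparison of death between groups in Tables 5 and 6 is biased against PAC only however death is treated elsewhere. Duration, persistence and the three-group log-rank test are affected to a smaller degree that depends on an unstated rule for deaths.

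The direction follows from the documents; the size does not. About 1.6- to 3.3-fold for 14-day death in heparin-first patients, and about 2-fold with half the cohort OAC-first, are illustrations under assumed mortality, bridging and time to OAC with no true difference.

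**What to change.** Keep Tables 5 and 6 as the description of all patients, so that short heparin courses stay in a primary objective. Then, in Protocol 9.3 and 9.7 and SAP 8.4 and 10:

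1. Report in-hospital deaths before day 14 for each cohort by first drug (heparin, warfarin, NOAC).
2. Present between-group death and persistence figures and the log-rank tests from a day-14 landmark. Fix groups by treatment received to day 14 among patients alive then; for persistence and the log-rank tests, require that they are also still on treatment.
3. State how death is handled in treatment duration and in the Kaplan-Meier curves.
4. Reword the classification sentence so that grouping uses the 2-week rule and the 30 days only bound the start of index treatment.

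This uses data already held. The cost is wording in both documents, a few table rows and one added analysis. The landmark results leave out patients who die before day 14 and, for persistence and the log-rank tests, those who stop before then. They therefore describe a selected group and must be labelled so.

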5. INTRODUCTION

Venous Thromboembolism (VTE), which includes deep vein thrombosis (DVT) and pulmonary embolism (PE), is a major cause of morbidity, mortality and healthcare expenditure. Although the occurrence of VTE in the Asian population has been lower than in Western populations, Its incidence has been reported to have increased rapidly in recent years.

For pharmacologic treatment of patients with VTE without cancer, the American College of Chest Physicians (CHEST) guidelines recommend the use of Non-Vitamin K antagonist oral anticoagulants (NOACs) over Vitamin K Antagonists (VKAs), with supporting evidences suggesting that each NOAC (e.g., apixaban) is effective at preventing recurrent VTE. In more recent treatment guidelines for the management of VTE released by the American Society of Hematology (ASH), NOACs are still recommended over VKAs for the initial management of VTE. NOACs are classified as new generation of anticoagulants with approved indications of the risk reduction of stroke and embolism in nonvalvular atrial fibrillation (NVAF) as well as prophylaxis and treatment of DVT and PE.

All NOACs became available as the first-line treatment of acute VTE in Korea after reimbursement expansion in May 2015. However, despite the increasing use of NOACs among VTE patients, there are still limited real-world evidence that assess treatment patterns as well as effectiveness and safety of the different anticoagulants especially among Asian population.

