Myocardial infarction
Stroke
Trauma
Previous use of medications (n, %)
Corticosteroids
NSAIDs
ACE inhibitors
Angiotensin II receptor blockers
Antiplatelets
β-blockers
Calcium-channel blockers
SSRI
Proton pump inhibitors
Diuretics
Thiazides
Vasodilators
Estrogens
Cyclooxygenase-2 inhibitors
Triazole antifungal agents
Outpatient visits (mean±std)

Table 4. Baseline characteristics among venous thromboembolism patients with active cancer by their index non-vitamin K antagonist oral anticoagulant treatment

Characteristics	Apixaban N= (%)	Dabigatran N= (%)	Edoxaban N= (%)	Rivaroxaban N= (%)	p-value
Follow-up (days; median, IQR)					
Age (years; mean±std)					
Age group (years; n, %)					
18-40					
40-65					
≥65					
Sex (n, %)					

Male

Female

Index VTE event (n, %)

DVT only

PE with or without

DVT

Health insurance type

(n, %)

National health

insurance

Medical aid

Veterans

Index year (n, %)

2013

2014

2015

2016

2017

2018

2019

CCI score (mean±std)

HAS-BLED score

(mean±std)

Comorbidities (n, %)

Antiphospholipid

syndrome

Asthma

History of cancer

COPD

Chronic kidney

disease

Chronic liver disease

Diabetes mellitus

Fracture

Heart failure

Hyperlipidemia

Hypertension

Ischemic heart

disease

Myocardial infarction

Stroke

Trauma

Previous use of

medications (n, %)

Corticosteroids

NSAIDs

ACE inhibitors

Angiotensin II

receptor blockers

Antiplatelets
β-blockers
Calcium-channel
blockers
SSRI
Proton pump
inhibitors
Diuretics
Thiazides
Vasodilators
Estrogens
Cyclooxygenase-2
inhibitors
Triazole antifungal
agents
Outpatient visits
(mean±std)

Table 5. Treatment pattern of anticoagulant therapy among venous thromboembolism patients without active cancer for the treatment groups of interest

	Warfarin-based therapy	NOAC-based therapy	PAC only
	N=	N=	N=
	(%)	(%)	(%)
Overall treatment duration (days)			
Mean, std			
Median, IQR			
3-month persistence (%)			
6-month persistence (%)			
Treatment switching (n,%)			
Mean, std			
Median, IQR			
Treatment continuation (n,%)			
Mean, std			
Median, IQR			
Treatment discontinuation (n,%)			
Mean, std			
Median, IQR			
Treatment interruption (n,%)			
Mean, std			
Median, IQR			
Death (n,%)			
Mean, std			
Median, IQR			

Note: PAC, parenteral anticoagulants; NOAC, non-vitamin K antagonist oral anticoagulant; IQR, Interquartile range; std, standard deviation

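### Phase I switching and treatment-continuation percentages have no time horizon, so they partly reflect when each group entered the cohort

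*SAP*

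**What the plan says.** On entry, SAP section 8.2 states: "The study cohort will be defined as patients diagnosed with VTE between 1 Mar 2013 and 30 Jun 2019". It adds: "The index date will be defined as the date of first prescription for anticoagulants within 30 days after the index VTE event". On follow-up in Phase I, Protocol section 4 states: "Patients will be followed-up from the index date until the earliest of in-hospital death or end of the study period (31 Dec 2019". There is no maximum per patient.

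On reporting, SAP section 10 and Protocol section 9.7 share the same wording. Numbers and percentages are planned for complete discontinuation and for patients who "experience treatment interruption and treatment switch during their follow-up will be described by the index anticoagulant treatment received". In SAP section 12, Tables 5-8 carry rows that open "Treatment switching (n" and "Treatment continuation (n", each with a percentage and no time point. Tables 9-12 give n (%) by the drug switched to, also with no time point. Continuation has no definition of its own. The nearest is the persistence rule in SAP section 8.4, which has no horizon.

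The plan also contains analyses that do use a time scale: Kaplan-Meier curves for time to interruption, switching and discontinuation, and persistence at 3 and 6 months, shown as rows in Tables 5-8.

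On calendar time, SAP section 5 states: "All NOACs became available as the first-line treatment of acute VTE in Korea after reimbursement expansion in May 2015".

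**The concern.** A percentage counted over all available follow-up means different things for patients observed for different lengths of time. Someone who started in March 2013 must stay on the drug for more than six years to be continuing at the cut. Someone who started at the end of June 2019 needs about six months. If the groups in a table entered at different times, their crude percentages differ even when patients behave identically: the later group shows more continuation and less switching.

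The groups probably did enter at different times. Warfarin could be an index drug from March 2013, whereas NOACs became first-line 26 months later. Describing switches and treatment patterns by index treatment is a primary Phase I objective, and SAP section 10 repeats all analyses by individual NOAC in order to identify differences in treatment patterns. Readers will compare these columns.

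**Working it through.** The plan states no figure for this point, so there is none to reproduce.

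**Potential follow-up (dates from the documents; one month = 365.25/12 = 30.4375 days)**
- Index 1 Mar 2013: 2,496 days = 82.0 months.
- Index 1 May 2015: 1,705 days = 56.0 months.
- Index 30 Jun 2019: 184 days = 6.05 months.
- Latest index, 30 Jul 2019 (30 days after the last diagnosis date): 154 days = 5.1 months.

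These are administrative limits; in-hospital death can shorten them.

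**Crude continuation under identical persistence**

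Assumptions not in the documents: exponential persistence with the same median in every group, uniform entry, index date equal to diagnosis date, no deaths. With h = ln 2/median, a = 6.05 months and b = 82.0 or 56.0 months, the expected crude percentage is the average of exp(−hF) over follow-up F between a and b:

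C = [exp(−ha) − exp(−hb)] / [h(b − a)]

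Median 6 months, h = 0.1155:
- From March 2013: (0.4974 − 0.0001)/(0.1155 × 75.95) = 5.7%.
- From May 2015: (0.4974 − 0.0015)/(0.1155 × 49.97) = 8.6%.

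Median 12 months, h = 0.0578:
- From March 2013: (0.7052 − 0.0088)/(0.0578 × 75.95) = 15.9%.
- From May 2015: (0.7052 − 0.0393)/(0.0578 × 49.97) = 23.1%.

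**Crude switching**

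If 20% of treatment ends are switches in every group (assumed), crude switching is 0.20 × (1 − C).

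| Assumed median | Continuation, from Mar 2013 | Continuation, from May 2015 | Switching, from Mar 2013 | Switching, from May 2015 |
|---|---|---|---|---|
| 3 months | 1.4% | 2.1% | 19.7% | 19.6% |
| 6 months | 5.7% | 8.6% | 18.9% | 18.3% |
| 12 months | 15.9% | 23.1% | 16.8% | 15.4% |
| 24 months | 34.0% | 44.4% | 13.2% | 11.1% |

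**Sensitivity to the assumptions**
- With a heavy-tailed Weibull (shape 0.5), continuation is 18.8% and 23.5% at a 6-month median, and 29.8% and 35.3% at 12 months. Switching at a 6-month median is 16.25% and 15.30%.
- If entry to the full-window group declines linearly to zero by June 2019, its exponential continuation falls to 1.3% (6-month median) or 6.8% (12-month median), which widens the gap.
- If some NOAC patients entered before May 2015, the gap narrows.

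The direction is the same in every case.

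**Analyses that are not affected**

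Every surviving patient can be observed to 3 months. Only index dates in July 2019 fall short of 6 months, about 1% of patients (0.5% with treatment lags spread over 0-30 days, 1.3% if every lag is 30 days). Kaplan-Meier handles the rest by censoring. In a simulation with identical 12-month median persistence and deliberately extreme entry patterns, it gave 70.5% at 6 months in both groups, against a true 70.7%.

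**The case against.** The strongest reply is that the plan already has the right tools. The same section plans Kaplan-Meier curves for each endpoint and persistence at 3 and 6 months, and the persistence rows sit in the criticised tables. Tables 1-4 show median follow-up and index year by group, so the imbalance is disclosed. Phase I is descriptive with no prior hypotheses, and Tables 5-12 have no p-value column. The continuation row may only be there to account for everyone.

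Much of this stands. A reader might infer that Phase I describes switching and continuation only through crude percentages; the documents do not support that. The reply still leaves two gaps. No time-to-event or fixed-time version exists for switch destination, and nothing tells the reader of Tables 5-8 that the persistence rows are comparable between groups while the continuation row is not. Reporting follow-up in another table discloses the problem but does not correct it. The statement that no comparisons will be made concerns the Kaplan-Meier analyses. It is followed by log-rank tests and by the stated aim of identifying differences between NOACs.

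A reader might also infer that a NOAC entering later would look better than another NOAC. The only Korean date given is common to the class, so a difference in entry between individual NOACs is not documented. Even May 2015 marks first-line reimbursement, not necessarily first use.

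**Conclusion.** The concern holds for the switching and continuation percentages in Tables 5-8 and for the switch-destination percentages in Tables 9-12. These depend on entry date, and the documents give a reason to expect different entry dates for warfarin-based and NOAC-based therapy.

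The size is conditional, because the plan gives no persistence curve or switch share. With the exponential model, uniform entry and NOAC entry from May 2015, the artefact in continuation is 2.9 percentage points at a 6-month median and 7.2 at 12 months. In switching, with a 20% switch share, it is about 0.6 and 1.4 points, and close to nothing at a 3-month median. A serious distortion of switching would need long persistence, which cannot be assumed. The planned Kaplan-Meier and fixed-time persistence results are sound on this point. The Phase II bleeding analyses, which use person-time and Cox models, are not touched. This is a worthwhile reporting correction, not a flaw in the design.

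**What to change.** In SAP section 10, Protocol section 9.7 and the shells for Tables 5-12:
- Report switching, overall and by destination, as cumulative incidence at 6 and 12 months from the index date. Treat discontinuation/interruption and death as competing events, and censor patients still on treatment at 31 Dec 2019. Under uniform entry, 182 of 2,313 entry days (7.9%) fall short of 12 months for the full window, and 182 of 1,522 (12.0%) from May 2015; censoring deals with these.
- Drop the continuation row in favour of the planned fixed-time persistence, or define it at the same horizons.
- At fixed horizons, combine interruption and discontinuation as end of first episode without switch, or apply one equal restart look-ahead to all patients. This is needed because SAP section 8.4 defines discontinuation by the absence of prescriptions over all remaining follow-up, which is shorter for later entrants.
- If whole-follow-up counts are kept, label them as not comparable between groups and show each group's median follow-up beside them. Removing the percentages alone would not help, since each column still shows its N.

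The cost is wording, table-shell edits, a decision on the combined or look-ahead definition, and some competing-risk programming. No new data are needed. Switches after 12 months leave the headline percentage but remain visible in the time-to-switch curves.
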